12 STATISTICAL CONSIDERATIONS

12.1 STUDY DESIGN & ENDPOINTS

A total of 300 subjects will be enrolled. Of those, we assume approximately 53% of the subjects (n=160) will have DNA shed and detectable ALK rearrangements, and will have progressed on either alectinib or ceritinib. Of the 160 subjects, we assume 80 subjects will have progressed on alectinib and 80 subjects will have progressed on ceritinib. Table 1 below shows the expected distribution of resistance mutations among these subjects.

Table 1: Expected distribution of resistance mutations

ALK mutation	Frequency after ceritinib	Frequency after alectinib
C1156Y	5%	0%
F1174X	15%	0%
I1171X	0%	10%
L1196M	0%	5%
G1202R	20%	30%
G1202del	5%	5%
D1203N	2%	0%
L1198F	5%	0%
C1156Y + L1198F	2%	2%
F1245C	0%	2%
No mutation	46%	46%

We will focus on two key mutational differences, F1174X and I1171X. With a type I error of 0.10, we have 99.8% power to detect the shown difference in acquiring the F1174X mutation, and 95.3% power to detect the shown difference in acquiring the I1171X mutation.

We will investigate response and time to treatment discontinuation (TTD) of those patients who have acquired an ALK mutation on their respective potential targeted therapy.

Table 2 below summarizes the maximum width of a 90% exact binomial confidence interval for response (CR+PR) to potential targeted therapy, per ALK mutation status.

Title: Study of Plasma Next Generation Sequencing for Remote Assessment, Characterization, Evaluation of Patients With ALK Drug Resistance (SPACEWALK)

Table 2: Max Width of 90% Exact Binomial Confidence Interval

ALK mutation	Total Sample Size	Number of Responses	Max Width of 90% CI
C1156Y	4	2	0.8043
F1174X	12	6	0.5093
I1171X	8	4	0.6143
L1196M	4	2	0.8043
G1202R	40	20	0.2779
G1202del	8	4	0.6143
D1203N	2	1	0.9491
L1198F	4	2	0.8043
C1156Y + L1198F	4	2	0.8043
F1245C	2	1	0.9491

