TTD is defined as the time from treatment start to treatment discontinuation for any reason, including disease progression, unacceptable toxicity, or death. For subjects who are alive without discontinuation, follow-up will be censored on the date of last adequate disease assessment. Table 3 below summarizes the intended TTD hazard ratios, median TTD improvement from 5 months, assuming exponential event time, power, and number of TTD events at full information with a Type I error of 0.10, for a total sample size of 10 or 20 subjects. TTD will be estimated using the Kaplan-Meier method and Cox proportional hazards models will be used to estimate hazard ratios. Comparisons of groups will be made using the log-rank test and Cox modeling.

Table 3: Time to Treatment Discontinuation

Total Sample Size	Number of events	Hazard Ratio	Median Survival	Median Survival After Therapy	1-Sided Type I Error Rate	Power
10	6	0.45	5 Months	12.5 Months	0.10	83%
20	14	0.50	5 Months	10 Months	0.10	89%

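### Time to treatment discontinuation is compared with large-sample log-rank and Cox methods although eight of ten mutation groups are expected to hold 2–8 subjects, and the groups to be compared are not named

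*Combined protocol and SAP*

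**What the plan says.** Section 12.1 estimates TTD by Kaplan-Meier and hazard ratios by Cox models, and then states: "Comparisons of groups will be made using the log-rank test and Cox modeling". No exact, permutation or other small-sample form is given, and the sentence does not say which groups are meant.

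The sizes come from Table 2 of the same section, which gives interval widths for "response (CR+PR) to potential targeted therapy, per ALK mutation status". Its totals are:
- 2 for D1203N and F1245C;
- 4 for C1156Y, L1196M, L1198F and C1156Y + L1198F;
- 8 for I1171X and G1202del;
- 12 for F1174X;
- 40 for G1202R.

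For response in these groups the plan uses exact binomial intervals.

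The error level appears with Table 3, introduced as "number of TTD events at full information with a Type I error of 0.10, for a total sample size of 10 or 20 subjects", with a column headed "1-Sided Type I Error Rate". The target there is a "median TTD improvement from 5 months, assuming exponential event time". Section 7.2 places outcome by resistance mechanism and later therapy among the secondary objectives.

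**The concern.** The usual log-rank p-value treats the standardised observed-minus-expected count as normal. With two or four subjects in one group and dozens in the other, that statistic is markedly skewed. The test then rejects too often in the direction where the small group stops treatment sooner, and too seldom in the direction where it stays on treatment longer. Wald limits from the Cox model share the problem.

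A rare mutation unrelated to TTD could therefore be reported as unfavourable more often than the nominal level suggests. A real advantage in carriers would be tested more strictly than intended. The plan guards against small numbers for response but not for TTD.

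**Working it through.** **1. What the 0.10 in Table 3 refers to.** With one-sided critical value 1.2816 and d events:
- Two groups, 1:1: power = Φ(√d/2 × |ln HR| − 1.2816). Six events at HR 0.45 give 38%, six at HR 0.40 give 44%, and 14 at HR 0.50 give 51%.
- One sample against a 5-month median: power = Φ(√d × |ln HR| − 1.2816). Six events at HR 5/12.5 = 0.40: 2.449 × 0.916 − 1.282 = 0.963, so 83.2%. Fourteen events at HR 0.50: 3.742 × 0.693 − 1.282 = 1.312, so 90.5% (89.9% with an exact exponential test).

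The printed powers are 83% and 89%. Table 3 is thus reproduced, to within 2 points, as a one-sample calculation and not as a two-group one. (Row 1 prints HR 0.45, which gives only 75%; that is a separate matter.) The 0.10 is therefore not an explicit level for mutation-group comparisons.

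**2. Inputs for the group comparison.**
- Group sizes from Table 2. The no-mutation group is 46% of 160, about 74 (Table 1).
- Exponential TTD with median 5 months in both groups (the Table 3 starting value).
- 24 months of accrual and 8 to 24 months of follow-up (section 12.2), so censoring is uniform on 8–32 months, capped at 24.
- Assumed: the pairings, and a nominal one-sided 0.10.

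**3. Hand check of the skew.** Beside a very large group and without censoring, a group of n has n events, and its expected count E is roughly a gamma variable with shape n. The statistic is about (n − E)/√E. For n = 2 it exceeds 1.2816 when E < 0.831, with probability 1 − e^(−0.831) × 1.831 = 20%. It falls below −1.2816 when E > 4.811, with probability e^(−4.811) × 5.811 = 5%. The same steps give 17% / 6% for n = 4 and 14% / 7% for n = 8.

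**4. Simulation of the asymptotic log-rank test under no difference** (20,000–60,000 data sets per pairing; simulation error about 0.3 points or less):

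| Sizes | Small group worse | Small group better |
|---|---|---|
| 2 vs 40 | 19–20% | 7% |
| 2 vs 74 | 20% | 6% |
| 4 vs 40 | 16% | 7–8% |
| 4 vs 74 | 16% | 7% |
| 8 vs 40 | 13% | 8–9% |
| 8 vs 74 | 13–14% | 8% |
| 12 vs 40 | 12% | 9% |
| 12 vs 74 | 12–13% | 8–9% |
| 40 vs 74 | 11% | 9–10% |
| 8 vs 12 | 12% | 10% |
| 5 vs 5 | 12% | 12% |
| 10 vs 10 | 11% | 11% |

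With 30–40% censoring, 2 vs 74 gives 18–19% / 6%. At unbalanced splits of the Table 3 totals, 2 vs 8 gives about 17.5% / 8.5% and 4 vs 16 about 15% / 8.6%.

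**5. Alternatives, same null** (worse / better):
- Permutation log-rank (2,500 data sets, 999 permutations): 2 vs 74, 9.8% / 9.7%; 4 vs 74, 10.0% / 10.9%; 8 vs 74, 10.0% / 10.4%; 2 vs 8, 8.4% / 9.2%. Simulation error is about 0.6 points.
- Cox Wald: 2 vs 40, 18% / 4%; 4 vs 40, 15% / 7%.
- Cox likelihood ratio: 2 vs 40, 15% / 9%; 4 vs 40, 13% / 9%; 8 vs 40, 12% / 10%.
- Cox with Firth's penalty, profile likelihood: 2 vs 40, 24% / 5–6%; 4 vs 40, 18% / 6%.

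The permutation test restores the level. The ordinary likelihood ratio is the best of the Cox options, and Firth's penalty is the worst.

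**The case against.** The strongest reply is that the large figures need a comparison the plan never specifies. The sentence names no groups. Section 12.1 introduces the TTD analysis for subjects who acquired a mutation, so the 74 without one are not a stated comparator. Table 3 concerns totals of 10 or 20. For the two mutations the plan singles out, I1171X and F1174X (8 vs 12), the error is about 12% / 10%. All of this stands, and it limits the claim.

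It does not remove it. Eight of the ten groups are tiny, so most comparisons by mutation would involve one. Every simulated pairing with a group of 12 or fewer exceeded 10% in at least one direction.

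A reader might also infer that the plan states a 10% error and delivers about 20%. The documents do not support that. The 0.10 belongs to Table 3, which behaves as a one-sample calculation for improvement. In that direction the unbalanced two-group test is conservative, at about 6–9%. The 20% concerns the opposite direction and only the two groups of 2.

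Finally, TTD serves a secondary objective in a study described as non-interventional (section 14.2.9), and no decision rule hangs on it. That stands too, and it is why the point is minor.

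**Conclusion.** The point holds in a limited form. Section 12.1 applies large-sample methods to groups that its own Table 2 expects to be very small, and leaves the comparisons undefined. At a nominal one-sided 0.10, the distortion beside a group of 40–74 or more runs from about 20% / 6–7% at n = 2 to 12% / 9% at n = 12. It is slight, about 11–12% both ways, for balanced groups of 5–10. These sizes rest on exponential TTD with a 5-month median, the section 12.2 follow-up, Table 2's expected counts, and pairings and a level that the plan does not state for this analysis. The finding is a missing specification and a poorly suited approximation in a secondary analysis; it does not touch the primary objective.

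**What to change.** In section 12.1, state which groups are compared with which, and at what level and sidedness. Then replace the comparison sentence by:

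> Comparisons of TTD between mutation groups will use the permutation (exact conditional) log-rank test; hazard ratios will be from a Cox model with profile-likelihood (likelihood-ratio) 90% limits, and comparisons involving the smallest groups (e.g. n=2) will be descriptive.

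Descriptive reporting suits the smallest groups because testing can be empty there: 2 vs 2 has only six possible allocations, so the smallest one-sided permutation p-value is 1/6 = 0.17. Firth's penalised likelihood should not be used for the limits. It keeps the hazard ratio finite but raises the error in the small-group-worse direction.

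Kaplan-Meier estimation stays as it is. The cost is a short text change and a few lines of code, with no added subjects or data. Comparisons between large groups barely change (40 vs 74 is already at about 11% / 9–10%).

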12.2 SAMPLE SIZE, ACCRUAL RATE & STUDY DURATION

The study duration will be 32 months: 24 months of accrual, and a minimum of 8 months of follow-up on the last subject enrolled, though subjects will be followed for a maximum of 24 months if the study remains enrolling or in follow-up. In **Table 4** are reflected the expected ethnic and racial distribution of the population to be included in the study.

Ethnic Category	Females	Males	Total
	Hispanic/Latino	20	10
Not Hispanic/ Latino	180	90	270

Title: Study of Plasma Next Generation Sequencing for Remote Assessment, Characterization, Evaluation of Patients With ALK Drug Resistance (SPACEWALK)

Ethnic Category: Total	200	100	300
Racial Category			
American Indian/Alaskan	10	5	15
Asian	30	15	45
African American	10	5	15
Hawaiian/ Pacific Islander	4	2	6
White	146	73	219
Racial Category: Total	200	100	300
Table 4. Expected ethnic and racial population distribution			

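### Table 3, row 1: medians of 5 and 12.5 months imply a hazard ratio of 0.40 under the stated exponential model, not the printed 0.45

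*Combined protocol and SAP*

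**What the plan says.** Section 12.1 introduces Table 3 as showing the target TTD hazard ratios with the matching "median TTD improvement from 5 months, assuming exponential event time, power, and number of TTD events at full information". The table has two rows, for 10 and 20 subjects, and a column headed "1-Sided Type I Error Rate" set at 0.10. In column order (subjects, events, hazard ratio, first median, median after therapy, error rate, power in percent) the rows are:

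- Row 1: "10 6 0.45 5 Months 12.5 Months 0.10 83"
- Row 2: "20 14 0.50 5 Months 10 Months 0.10 89"

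The text names Kaplan-Meier estimation, Cox models and the log-rank test for the analysis. It does not say which test or formula produced the power column. Section 12.2 gives the study timing: "24 months of accrual, and a minimum of 8 months of follow-up on the last subject enrolled", with each subject followed for at most 24 months.

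**The concern.** An exponential distribution has a constant hazard equal to ln 2 divided by its median, so the ratio of two hazards is the inverse ratio of the medians. Once the plan adopts that model, the hazard ratio and the two medians in a row are not free of each other. Row 2 follows the rule and row 1 does not.

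Section 8.1 chooses TTD as the measure of benefit because prospective CT-based response assessment is not feasible with remote participation. Table 3 is the plan's only statement of the size of TTD effect it can detect. For 10 subjects the reader is given two effects and cannot tell which one carries the 83% power.

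**Working it through.** **Inputs.** Medians, hazard ratios, event counts, one-sided error of 0.10 and power come from Table 3. The exponential model comes from the text introducing it. Accrual of 24 months, minimum follow-up of 8 months and the 24-month maximum come from section 12.2. Uniform accrual and a TTD clock starting at enrolment are assumptions made here.

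**Step 1. The identity.** Hazard ratio = first median / median after therapy.

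- Row 2: 5/10 = 0.50. Printed 0.50, reproduced.
- Row 1: 5/12.5 = 0.40. Printed 0.45, not reproduced.
- Median implied by 0.45: 5/0.45 = 11.1 months.
- First median implied by 0.45 if 12.5 is kept: 0.45 × 12.5 = 5.6 months.

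Rounding does not close the gap. Medians read to the nearest 0.1 month give 4.95/12.55 = 0.394 to 5.05/12.45 = 0.406. Even a first median anywhere from 4.5 to 5.5 months over 12.5 reaches only 0.36 to 0.44.

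**Step 2. Event counts.** With λ = ln 2/median, accrual A = 24 and minimum follow-up F = 8, the probability of an observed event is

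p = 1 − [exp(−λF) − exp(−λ(A+F))]/(λA).

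For a median of 12.5 months, λ = 0.0555 and p = 1 − (0.642 − 0.170)/1.331 = 0.645. The results are:

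| Row | Median | Expected events | With the 24-month cap | Printed |
|---|---|---|---|---|
| 1 (n = 10) | 12.5 | 6.45 | 6.28 | 6 |
| 1 (n = 10) | 11.1 | 6.85 | 6.69 | 6 |
| 2 (n = 20) | 10 | 14.40 | 14.11 | 14 |

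With ordinary rounding, both printed counts follow from the printed medians, while 11.1 months would give 7. No power formula enters this step.

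**Step 3. Power.** The method is not stated. A one-sample exponential test against a fixed 5-month median has power Φ(√d × |ln HR| − 1.2816) with d events at one-sided 0.10. For 6 events at 0.40 this is Φ(2.449 × 0.916 − 1.2816) = Φ(0.963) = 83.2%. The exact chi-square version is P(χ² with 2d df > HR × its 90th percentile).

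| Events | Hazard ratio | Normal | Exact | Printed |
|---|---|---|---|---|
| 6 | 0.40 | 83.2% | 82.9% | 83% |
| 6 | 0.45 | 75.0% | 75.7% | 83% |
| 14 | 0.50 | 90.5% | 89.9% | 89% |

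Solving for the hazard ratio that gives 83% with 6 events returns 0.401 (normal) or 0.399 (exact). Row 2 is matched only approximately. An equal two-group log-rank test with 6 events has about 44% power at 0.40 and 38% at 0.45, so it does not explain the table.

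**The case against.** The mismatch itself has no good defence: the row is legible, nothing is redacted, and no other section accounts for it. What can be disputed is which cell is wrong.

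- **Event counts.** If counts were truncated instead of rounded, 11.1 months also gives 6. The check also starts the clock at enrolment, whereas section 12.1 measures TTD from the start of treatment. With an assumed one-month lag and the 24-month cap, 11.1 months gives 6.48, which rounds to 6, and row 2 gives 13.69, which rounds to 14. A gap of about 0.4 expected events is thin evidence.
- **Choice of test.** The one-sample test is inferred. It takes the printed 6 events as given; with the 6.28 to 6.45 expected at 12.5 months it gives about 84% to 85% at 0.40. Simulated one-sample log-rank tests using the plan's accrual and censoring give about 81% to 84% at 0.45 and 87% to 90% at 0.40. On that approach the printed 83% lies nearer 0.45.
- **Importance.** Table 3 sets no decision rule, stopping boundary or sample size.

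These points stand as limits on the attribution. They do not reverse it, because the log-rank variants give 92% to 93% for row 2 against the printed 89%. Of the methods tried, the one-sample exponential test with 0.40 in row 1 comes closest on both rows taken together. The figure 12.5 is also exactly 5/0.40. The point about importance is accepted and bounds the consequence.

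**Conclusion.** The concern holds. Under the plan's own model, the hazard ratio and medians in row 1 cannot both be right: 0.40 against 0.45, or equivalently 12.5 against 11.1 months. This needs no assumption beyond the stated exponential distribution.

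That the hazard ratio cell is the faulty one is likely but not proven. It rests on an inferred power method, uniform accrual, rounded event counts and a clock starting at enrolment. On this reading, the effect that carries 83% power with 10 subjects is a 60% hazard reduction, not 55%, and the power cell need not be wrong. If 0.45 was intended, power depends on the unstated method: about 75% with 6 events under the inferred test, and about 81% to 84% under the log-rank variants.

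The row should be corrected, but the effect is confined to this power statement. The sample size of 300, the primary objective and the TTD analysis methods are untouched.

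**What to change.** Change the hazard ratio in Table 3, row 1, from 0.45 to 0.40, and leave 6 events, 12.5 months and 83% as printed. If the study team's records show that 0.45 was intended, change the median to 11.1 months instead, and recompute the event count (about 7) and the power with the method actually used.

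In either case, add a clause to the text introducing Table 3 that names the power method and says whether it is a one-sample test against a fixed 5-month median or a comparison of two groups.

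The cost is one table cell and one clause. Keeping 0.45 means rechecking three cells. No change to conduct, data collection or enrolment follows.

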12.2 SAMPLE SIZE, ACCRUAL RATE & STUDY DURATION

The study duration will be 32 months: 24 months of accrual, and a minimum of 8 months of follow-up on the last subject enrolled, though subjects will be followed for a maximum of 24 months if the study remains enrolling or in follow-up. In **Table 4** are reflected the expected ethnic and racial distribution of the population to be included in the study.

Ethnic Category	Females	Males	Total
	Hispanic/Latino	20	10
Not Hispanic/ Latino	180	90	270

Title: Study of Plasma Next Generation Sequencing for Remote Assessment, Characterization, Evaluation of Patients With ALK Drug Resistance (SPACEWALK)

Ethnic Category: Total	200	100	300
Racial Category			
American Indian/Alaskan	10	5	15
Asian	30	15	45
African American	10	5	15
Hawaiian/ Pacific Islander	4	2	6
White	146	73	219
Racial Category: Total	200	100	300
Table 4. Expected ethnic and racial population distribution			

13 DATA COLLECTION AND ANALYSIS

The Principal Investigator is responsible for assuring the accuracy, completeness and timeliness of all study documentation.

13.1 CASE REPORT FORMS

See section 10.5 for a description of clinical data to be collected and maintained within the ALCMI Data Repository.

13.2 SOURCE DOCUMENTS

Source documents are considered to be original subject records that may be in the form of lab, pathology or imaging reports. Source documents are considered to be adequate when they are presented in final form; documents which are unsigned by hand or electronically are considered to be preliminary.

All PHI is to be redacted from all source documents, such as histopathology or imaging reports. Subject identifiers will be inserted onto the required source documents entered into the ALCMI Data Repository.

13.3 MONITORING

The Principal Investigator is responsible for the overall conduct of the study and other tasks detailed in section 14.1.

Title: Study of Plasma Next Generation Sequencing for Remote Assessment, Characterization, Evaluation of Patients With ALK Drug Resistance (SPACEWALK**)**

Once the study is initiated, the ALCMI Study Manager or designee will maintain regular contact with the Investigator and the site's assigned study staff by periodic on-site or remote visits, telephone calls, letters, e-mails and FAX transmissions. The purpose of this communication is to: confirm IRB approval of the study, track study enrollment, occasionally assess adherence to the study protocol and act as a resource to the study staff. Any enrollment, specimen collection or shipment issues should immediately be reported to the Study Manager or designee. The Study Manager or designee will work with the site and ALCMI's bio- and data repository staff to make any arrangements required to evaluate and correct problems.

If the study requires, quality assurance monitoring visits from ALCMI or an ALCMI representative may be carried out to review study plan compliance, compare entries of the electronic case report forms with individual subjects' medical records, and perform accounting of study material. Site personnel should ensure ample time is scheduled to review data clarifications, protocol questions, and/or any data issues that may have surfaced prior to or during study conduct.

13.4 INTERIM ANALYSIS PLAN

An interim analysis of the study will be performed after 50, 100, and 200 subjects are enrolled. The analysis will include a review of the study's feasibility, enrollment rate, detection rate in the study population and to update our understanding of drug resistance reporting strategies. The analysis will include DFCI members, ALCMI representatives and may involve a steering committee of ALCMI investigators as needed.

13.5 DATA & SAFETY MONITORING

We will conduct data and safety monitoring, as is outlined within DFCI's overall Data Safety Monitoring Plan (DSMP). The Principal Investigator and study staff are familiar with and will adhere to steps outlined within the DSMP. All research conducted for this study will undergo human subject's review at DFCI. Clinical research coordinators or other staff members will be assigned to the study as needed. The responsibilities of the site staff include study compliance, data collection, abstraction and entry, data reporting, regulatory monitoring, problem resolution and prioritization, biospecimen kit shipment, and coordination of the activities of the study team.

13.6 PUBLICATION PLAN

The results should be made public within 24 months of reaching the end of the study. The end of the study is the time point at which the last data items are to be reported, or after the outcome data are sufficiently mature for analysis, as defined in the section on Sample Size, Accrual Rate and Study Duration. If a report is planned to be published in a peer-reviewed journal, then that initial release may be an abstract that meets the requirements of the International Committee of Medical Journal Editors. A full report of the outcomes should be made public no later than 3 years after the end of the study.

14 STUDY MANAGEMENT

14.1 STUDY RESPONSIBILITIES

ALCMI will be responsible for the following:

**Title: Study of Plasma Next Generation Sequencing for Remote Assessment,
Characterization, Evaluation of Patients With ALK Drug Resistance (**SPACEWALK**)**

- Online informed consent, subject registration, data and biospecimen collection and tracking systems;
- Centralized biospecimen and data storage;
- Act as a resource to the study staff;
- Facilitating cross-institutional collaboration processes within the ALCMI consortium.

Investigator will be responsible for the following:

- Ethical and safety considerations;
- Ensure IRB review and approval are obtained and maintained;
- Ensure that any reviewing IRB is promptly informed of significant new information about the investigation;
- Conducting study in accordance with Good Clinical Practices and with applicable regulatory requirements;
- Study staff's adherence to protocol requirements;
- Collection of sufficient quality and quantities of biospecimens;
- Accurate and timely completion of case report forms;

